# SCHEMATIC OF STUDY ENROLLMENT

# SCHEMATIC OF GENETIC SCREENING PHASE

# SCHEDULE OF STUDY VISITS AND PROCEDURES: VISION COHORT 1 & VISION COHORT 2

Visit	Screening	Baseline	12M	24M	36M	48M
Visit Target Windows	(Up to Day	(Day 0) b	Wk	Wk	Wk	Wk
	-60) a		$52 \pm 4^{\circ}$	$104 \pm 4^{c}$	156± 4°	208± 4°
Participant-Level Procedures						
Informed Consent / Eligibility Assessment	Х					
Demographics/Screening Medical History (including pre-existing conditions,	X					
symptomology history, patient-reported daily activities, and medications)	Λ					
Determination of Vision Cohort	X					
3mm punch skin biopsy i		Х				
Concomitant Medications	Х	Х	Х	Х	Х	Х
Adverse Events		Х	Х	Х	Х	Х
Patient Reported Outcomes (PROMIS-29, MRDQ, ViSIO-PRO, LVP-FVQ II) h		Х		Х		Х
Ocular Procedures - All testing performed in each eye						
Complete Ophthalmic Exam f	Х		Х	Х	Х	Х
Intraocular Pressure g	Х		Х	Х	X	Х
Visual acuity (including refraction, ETDRS, BRVT if needed, LLVA if needed)	Х		Х	Х	X	Х
SD-OCT volume scans (Heidelberg Spectralis)		Х	Х	Х	Х	Х
SD-OCT vertical and horizontal scans (Heidelberg Spectralis)		Х	Х	Х	Х	Х
Axial Length and Corneal Curvature measurements		Х		Х		Х
Fundus Autofluorescence (FAF) (Optos)		Х	Х	Х	Х	Х
Ultra-Widefield Color Photo (Optos)		Х	Х	Х	Х	Х
Optical coherence tomography angiography (OCTA) j		Х	Х	Х	Х	Х
Red reflex photo k		Х	Х	Х	Х	Х
Full-field Stimulus Threshold (Diagnosys Espion)		Х	Х	Х	Х	Х
Static perimetry (Octopus 900 Pro)		X d	Х	Х	Х	Х
Fundus guided microperimetry (MAIA)		X d	Х	Х	Х	Х
Kinetic VF III4e for Vision Cohort definition only	Xe					

**a.** All Screening Visit testing must be completed on the same day (except for kinetic VF, as noted below).

b. Baseline Visit date (defined as the start date of all Baseline testing) must be no later than two (2) weeks after receiving confirmation of meeting *final study cohort criteria* from the CGA. All Baseline testing must be completed within ten (10) days of the Baseline Visit date, except PROs as specified.

c. All Follow up visit testing must be completed on the same day, except PROs as specified.

**d.** For static perimetry and microperimetry, all Vision Cohort 1 and 2 participants will complete two (2) tests at baseline. The results will be compared according to the *visual field criteria* to determine if a third test is needed.

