**e.** Historical measurement performed within the last eighteen (18) months prior to the Screening Visit. If a historical measurement is not available, then perform the Kinetic VF III4e at the Screening Visit.

f. Ophthalmic exam includes slit-lamp biomicroscopy and indirect ophthalmoscopy. Whenever possible the site should make its best effort to ensure that the exam takes place at approximately the same time of the day at each visit and with the same equipment.
g. IOP measurements will be taken prior to pupil dilation.

**h.** PROs may be completed in person or remotely any time within six (6) months of the Baseline visit or any time within the allowable window of the associated visit window (not required to be the same day as the rest of the visit). Required PROs depend on age, see outcomes grid.

i. Collected by certified investigator; sent to JHU/KKI Biochemical Genetics Lab.

**j.** If site does not have the equipment that would be required for the ancillary study, then participation in this test will be waived, with approval from the Coordinating Center. Site must use a pre-approved equipment for this test.

**k.** Digital camera capable of capturing external eye photos, Megapixels of >=3MP, Magnification of 30-40 degrees, Digital camera export in PNG, TIF, DICOM or BMP.

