558 559 560 561 562 563	detailed in and certif	wing procedures will be performed at the Baseline Visit. The testing procedures are in the GYROS Clinical Site Manual of Procedures . An overview of the equipment fication requirements for all testing is in Chapter 5.1: Study Procedure nents . All ocular testing will be performed in each eye, OD first and then OS. Baseline es will last approximately seven $(7) - eight (8)$ hours. Baseline procedures will span 10) days.
564	3.3.1	Baseline Data Collection and Testing Cohorts 1 & 2
565	1.	Medical updates to include:
566		• New or changed adverse events (AEs)
567		New ocular procedures
568		New or changed medications
569		• Request medical records and laboratory records if applicable.
570	2.	Patient Reported Outcomes
571		
 
Adults: PROMIS®-29, MRDQ, ViSIO-PRO
 

572		
 
Adolescents: LPV-FVQ II, ViSIO-PRO
 

573		Children: LPV-FVQ II
574 575 576		• The PROs may be completed in person or remotely (phone or other remote methods) any time within six (6) months of the Baseline Visit (not required to be the same day as the rest of the Baseline Visit).
577	3.	Skin biopsy (3mm punch skin biopsy)
578		• Ship to Johns Hopkins University Department of Genetic Medicine Research Lab
579	4.	Spectral Domain Optical Coherence Tomography (SD-OCT)
580		Volume Scan
581		Vertical and Horizontal Scan
582	5.	Axial Length and Corneal Curvature Measurements
583	6.	Fundus Autofluorescence
584	7.	Widefield color photo

585	8. Optical coherence tomography angiography (OCTA)
586	• Ancillary test; may be waived with approval from the Coordinating Center
587	9. Red reflex photo
588	10. Full field Stimulus Threshold (FST)
589	11. Static perimetry
590 591	• Two (2) tests will be performed. The clinical site will compare the certified technician determined mean sensitivity from test one (1) versus test two (2).
592 593 594 595	
 
(a) If the absolute value of the difference between the two tests is ≤ 2.4 dB, then the participant passes static perimetry reliability criteria. A third test is not needed.
 

596 597 598	(b) If the absolute value of the difference between the two tests is > 2.4 dB, then the participant does not pass static perimetry reliability criteria. A third test will be required .
599	12. Fundus guided microperimetry

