### 650 **4.2 Target Timelines**

- Target dates and windows for each study Follow-up Visit for all vision cohorts are shown below.
- Dates and windows are timed from Baseline Visit Date. Visits will be scheduled in the target window.

### 654

Table 4-1. Schedule for Follow-up Visits

VISIT SCHEDULE	TARGET DATE	TARGET WINDOW (AROUND TARGET DATE)
12 Month Visit	52 Weeks	± 4 Weeks
24 Month Visit	104 Weeks	± 4 Weeks
36 Month Visit	156 Weeks	± 4 Weeks
48 Month Visit	208 Weeks	$\pm 4$ Weeks

655 656

Table 4-2. Schedule for Remote Blood Spot Collection

BLOOD SPOT SCHEDULE	TARGET DATE	TARGET WINDOW (AROUND TARGET DATE)
4 Months	17 Weeks	± 4 Weeks
8 Months	34 Weeks	± 4 Weeks
16 Months	69 Weeks	± 4 Weeks
20 Months	86 Weeks	$\pm 4$ Weeks
28 Months	121 Weeks	± 4 Weeks
32 Months	138 Weeks	$\pm 4$ Weeks
40 Months	173 Weeks	± 4 Weeks
44 Months	190 Weeks	$\pm$ 4 Weeks

The goal will be for all participants to complete all scheduled visits. However, participants who,

because of unforeseen circumstances, are unable or unwilling to return for all follow-up visits

659 will be permitted to return for key visits only as an alternative to withdrawal from the study.

660 Additional office visits may occur as needed.

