736	2. Patient Reported Outcomes

737	
 
Complete at 24-Month and 48-Month Follow-up Visits Only
 

738	
 
Adults: PROMIS®-29, MRDQ, ViSIO-PRO
 

739	
 
Adolescents: LPV-FVQ II, ViSIO-PRO
 

740	Children: LPV-FVQ II
741 742 743	• The PROs may be completed in person or remotely (phone or other remote methods) any time within the Allowable Window of the associated visit, (not required to be the same day as the rest of the Follow up Visit).
744	3. Complete ophthalmic examination to include:
745	Slit lamp biomicroscopy
746	Indirect ophthalmoscopy
747	4. IOP
748	• IOP measurements will be taken prior to pupil dilation.
749	5. VA (including refraction, ETDRS, BRVT if needed, LLVA if needed)
750 751 752	• The visual acuity letter score will determine whether LLVA or BRVT will be performed. The criteria are defined in the GYROS Clinical Site Manual of Procedures.
753	6. SD-OCT
754	Volume Scan
755	Vertical and Horizontal Scan
756	7. Axial Length and Corneal Curvature Measurements
757	Complete at 24-Month and 48-Month Follow-up Visits Only
758	8. Fundus Autofluorescence
759	9. Widefield color photo
760	10. OCTA
761	• Ancillary test; may be waived with approval from the Coordinating Center
762	11. Red reflex photo
763	12. Full field Stimulus Threshold test (FST)
764	13. Static perimetry
765	14. Fundus guided microperimetry
766	15. Measurements to include:
767	• Weight
768	• Height
769	• Measured annually in participants <21 years of age at enrollment.

770 4	4.4.2 F	ollow-up Data Collection and Testing Cohort 3
771	1.	Medical updates to include
772		• New or changed adverse events (AEs)
773		New ocular procedures
774		New or changed medications
775		
 
Request medical records and laboratory records if applicable
 

776	2.	Patient Reported Outcomes
777		Complete at 24-Month and 48-Month Follow-up Visits Only
778		Adults: PROMIS®-29, MRDQ, ViSIO-PRO
779		
 
Adolescents: LPV-FVQ II, ViSIO-PRO
 

780		Children: LPV-FVQ II
781 782 783		• The PROs may be completed in person or remotely (phone or other remote methods) any time within the Allowable Window of the associated visit, (not required to be the same day as the rest of the Follow up Visit).
784	3.	Complete ophthalmic examination to include:
785		Slit lamp biomicroscopy
786		Indirect ophthalmoscopy
787	4.	IOP
788		• IOP measurements will be taken prior to pupil dilation.

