### 1150 8.3.1 Primary Objective Analysis

1151 The primary objectives of the natural history study and brief analysis plan for each are as 1152 follows.

**1.** Natural History 1153 (a) Characterize the natural history of retinal degeneration associated with 1154 disease-causing OAT variants over four (4) years, as measured using 1155 functional, structural, and patient-reported outcome measures. 1156 1157 i. Functional and structural measures: The distribution of each 1158 outcome at each visit will be summarized (including tabulating 1159 categorically, as well as means, SDs, medians, quartiles, ranges; both 1160 the absolute change and percent change will be evaluated, tests 1161 performed multiple times per visit will be analyzed using the average 1162 of all available tests). To determine the average annual rate of 1163 progression in the population for each outcome, a mixed effects model 1164 will be fit using all available outcome data at baseline and all annual 1165 visits. Both the correlation in outcomes over time and the correlation 1166 in outcomes between eyes will be accommodated by the model. 1167 Mixed models adequately accommodate missing values when missing 1168 values are missing at random (MAR). A second method of 1169 accommodating missing values will be through multiple imputation for 1170 the outcome values for all missing time points (including participants 1171 who discontinue follow up prior to forty-eight (48) months). 1172 Secondary analyses using binary definitions of outcome measures will 1173 also be explored in time to event analyses; Kaplan-Meier estimates 1174 with 95% confidence intervals will be calculated. 1175 1176 **PRO measures:** The scoring of each questionnaire will be completed ii. 1177 according to the procedures recommended by the developers of the 1178 questionnaire for each instrument. Baseline scores will be cross 1179 tabulated with categorical (severity of disease) versions of the outcome 1180 measures of interest at baseline. Changes in scores will be cross 1181 tabulated with binary (progression of disease) versions of the outcome 1182 measures of interest at the 24- and 48-month visits. A generalized 1183 linear model adjusted for baseline differences will be explored. 1184

1185	Partially completed questionnaires will be managed using methods
1186	recommended by the developers of the specific questionnaire. When
1187	no questionnaire is completed, we will use statistical methods that

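### Baseline PROs may be completed within six months of the Baseline Visit, so a nominal 24-month PRO change can cover about 18 months

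*Protocol*

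**What the plan says.** **Baseline PROs.** Section 3.3.1 (Cohorts 1 and 2) and Section 3.3.2 (Cohort 3), item 2 in each, allow completion "any time within six (6) months of the Baseline Visit". Footnote h of the Cohort 1 and 2 schedule and footnote g of the Cohort 3 schedule repeat the rule. None of the four says whether the six months run before the visit, after it, or both.

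**Other Baseline Visit tests.** Footnote b of both schedules requires completion within ten "days of the Baseline Visit date, except PROs as specified". PROs are therefore a named exception. Visual acuity, intraocular pressure and the ophthalmic examination are not in the Baseline column. Their baseline values come from Screening, up to 60 days earlier.

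**Follow-up.** Section 4.2 states: "Dates and windows are timed from Baseline Visit Date". Table 4-1 puts the 24-month visit at week 104 and the 48-month visit at week 208, each with a target window of ±4 weeks. For PROs, Sections 4.4.1 and 4.4.2 say "Complete at 24-Month and 48-Month Follow-up Visits Only" and allow completion "any time within the Allowable Window of the associated visit". The footnotes use the same term. The protocol gives target windows only and never defines an allowable one.

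**Analysis.** Section 8.3.1, 1(a)ii, sets baseline scores against baseline disease severity. Changes in score are "tabulated with binary (progression of disease) versions of the outcome" measures at the 24- and 48-month visits.

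**The concern.** Objective 1a includes progression on patient-reported outcomes. The study's stated impact includes finding which measures are most sensitive to change and choosing time points for a future trial. Both need PRO change and ocular change to cover about the same period.

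A late baseline questionnaire shortens the PRO interval and leaves the imaging and perimetry intervals as they were. With only two post-baseline PRO visits, no intermediate measurement makes up for the lost time. PROs could then look less responsive for reasons of timing alone. A baseline score could also be tabulated against severity measured up to six months apart from it, and a score change against ocular progression over a longer period.

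**Working it through.** The protocol states no figure for the PRO interval, so there is none to reproduce. The check is calendar arithmetic.

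**Inputs**
- One month = 365.25 / 12 / 7 = 4.348 weeks, so six months = 26.1 weeks (3.3.1, 3.3.2, footnotes h and g).
- 24-month visit at week 104 ± 4; 48-month visit at week 208 ± 4 (Table 4-1).
- Other Baseline Visit tests within 10 days = 1.4 weeks of the date testing starts (footnote b).
- Assumption: because the Allowable Window is undefined, the ±4-week target window is used for follow-up PROs.

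**Step 1. Interval = follow-up week − baseline PRO week**

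| Baseline PRO | 24M, early edge (wk 100) | 24M, target (wk 104) | 48M, early edge (wk 204) | 48M, target (wk 208) |
|---|---|---|---|---|
| Day 0 | 100 wk (23.0 mo) | 104 wk (23.9 mo) | 204 wk (46.9 mo) | 208 wk (47.8 mo) |
| +6 months | 73.9 wk (17.0 mo) | 77.9 wk (17.9 mo) | 177.9 wk (40.9 mo) | 181.9 wk (41.8 mo) |
| −6 months | 126.1 wk (29.0 mo) | 130.1 wk (29.9 mo) | 230.1 wk (52.9 mo) | 234.1 wk (53.8 mo) |

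The last row applies only if the wording also permits completion before Baseline.

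**Step 2. Comparison with tests done at the Baseline Visit.** At the week-104 target these span 104 − 1.4 = 102.6 to 104 weeks, against 77.9 weeks for a PRO completed at +6 months. At the early edge they span 98.6 to 100 weeks, against 73.9. The PRO shortfall is the same in both cases, 24.7 to 26.1 weeks. The four weeks lost by an early follow-up visit shorten both intervals and are not part of the discrepancy.

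**Step 3. Understatement due to the late baseline, assuming linear change**
- Completed at the visit: 0 at both time points.
- Completed at +6 months: 26.1 / 104 = 25% at 24 months; 26.1 / 208 = 12.5% at 48 months.
- Dates spread evenly over 0 to 6 months (an assumption), mean delay 3 months: 3 / 24 = 12.5% at 24 months; 3 / 48 = 6.25% at 48 months.

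**Step 4. Size on the protocol's own scale.** Section 8.2.4 assumes a decline of 5% per year. If PROs followed that rate (an assumption), a three-month delay removes 0.25 × 5 = 1.25 percentage points and a six-month delay 0.5 × 5 = 2.5 points. The planned 95% confidence interval half-width with 40 participants is 6%.

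**The case against.** The exception is deliberate. Footnote b announces it, and the same six months appears in all four places. A reader might infer that the protocol contradicts itself; it does not. PROs are also not among the outcomes labelled primary.

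A reader might also infer that every baseline measure except the PROs is held to ten days. That is not so: acuity, pressure and the examination are taken at Screening. The study thus already accepts baselines from different dates. This weakens the contrast for acuity but does not remove it. The Screening offset is at most 60 days and lengthens the acuity interval, while a late PRO shortens its own by up to six months. Imaging and perimetry do fall under the ten-day rule.

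The real effect is unknown. No completion dates are given, PROs sit in the Baseline column of the schedule, and if most are done at the visit the bias is close to zero. Completion before Baseline would act in the opposite direction. The possible losses in Step 4 are also smaller than the planned half-width. All of this stands and limits the claim. The half-width, however, describes random error and would not reveal a systematic shortfall in one group of measures.

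Finally, Chapter 8 is only a framework, and mixed models for the PROs could use actual dates. That is fair for estimated rates, and a missing analysis detail is not the complaint here. The collection window is a protocol rule. Modelling dates would not bring a late baseline score closer to the severity measure it is tabulated against, and it would not align the cross-tabulations by visit.

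**Conclusion.** The point holds as a badly fixed collection window. Followed as written, the rule lets a 24-month PRO change cover about 18 months at the target visit date and a 48-month change about 42 months. The figures of 17 and 41 months need both the last permitted day after Baseline and the early edge of the follow-up window, so they should not be read as typical.

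Under linear change the understatement lies between 0 and 25% at 24 months and between 0 and 12.5% at 48 months. The averages of 12.5% and 6.25% depend on an assumed even spread of dates after Baseline; a reader might take them as expected bias, but nothing in the protocol supports that spread. All these figures take the ±4-week target window as the follow-up PRO window. A wider Allowable Window would loosen the other end of the interval as well.

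The change is worth making because the comparison at risk, responsiveness of PROs against imaging and perimetry, is one the study exists to inform, and because the remedy is cheap.

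**What to change.** 1. In Sections 3.3.1 and 3.3.2 and footnotes h and g, shorten the baseline PRO window and state its direction, for example ±4 weeks of the Baseline Visit date. Remote completion is already allowed, and Section 5.2 puts each questionnaire at about fifteen minutes, so a shorter window is workable.
2. In Sections 4.4.1 and 4.4.2 and footnotes h and g, define the Allowable Window or refer to the Table 4-1 window. If something wider than the target window was meant, state it.
3. Specify the actual PRO completion date as the time variable in the PRO models, in Section 8.3.1 or the SAP.
4. Keep baseline PROs completed outside the new window in the data. In the nominal 24- and 48-month cross-tabulations show those participants separately rather than dropping them; with a goal of 45 participants, exclusion would waste information.

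The cost is wording edits in six places (3.3.1, 3.3.2, 4.4.1, 4.4.2, footnotes h and g), the analysis statement in item 3, and a few more baseline questionnaires flagged as late.

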600 601	• Two (2) tests will be performed. The clinical site will compare the certified technician determined mean sensitivity from test one (1) versus test two (2).
602 603 604 605 606	(a) If the absolute value of the difference between the two tests divided by the average between them is $\leq 50\%$ OR the absolute value of the difference between the two tests is $\leq 0.5$ dB, then the participant passes the microperimetry reliability criteria. A third test is not needed .
607 608 609 610	(b) If the absolute value of the difference between the two tests divided by the average between them is $> 50\%$ AND the absolute value of the difference between the two tests is $> 0.5$ dB, then the participant does not pass microperimetry reliability criteria. A third test will be required .
611	13. Measurements to include:
612	
 
Weight
 

613	♦ Height
614	3.3.2 Baseline Data Collection and Testing Cohort 3
615	1. Medical updates to include
616	• New or changed adverse events (AEs)
617	New ocular procedures
618	
 
New or changed medications
 

619	• Request medical records and laboratory records if applicable.
620	2. Patient Reported Outcomes
621	
 
Adults: PROMIS®-29, MRDQ, ViSIO-PRO
 

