# 1032 8.2.1 Sample Size Considerations for Evaluating Percent Change from Baseline to four 1033 (4) Years – All Outcomes

1034 Longitudinal changes on all outcome parameters being collected will be examined with the

1035 change in preserved retina being of particular interest. Change from baseline to four (4) years

1036 will be evaluated for sample size purposes, although statistical analyses will include the data

1037 from each annual visit. The power and sample size calculations below may be used to consider

1038 percent change on any outcome measure from baseline to four (4) years.

1039 Both eyes of a participant will be assessed for the main outcomes of interest. Thus, if there are N

1040 participants, 2N eyes will be available for analysis. However, outcome measures from two (2)

1041 eyes of a person are typically strongly correlated ( $r \ge 0.5$ ). The contribution of information from

1042 the two (2) eyes in this case is (2/(1+r)) instead of two (2). Values for the multiplier to the

1043 number of participants to obtain an effective sample size are given below:

r	Effective N
0.0	2.00
0.1	1.82
0.2	1.67
0.3	1.54
0.4	1.43
0.5	1.33
0.6	1.25
0.7	1.18
0.8	1.11

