# Table 6.1. Sample size versus half width of 95% confidence interval for the mean percent change for varying standard deviation values.

	Effective Sample Size (N of participants)				
	n=11 (10)	n= 22 (20)	n= 33 (30)	n= 44 (40)	n=55 (50)
SD=20%	12%	8%	7%	6%	5%
SD=30%	18%	13%	10%	9%	8%
SD=40%	24%	17%	14%	12%	11%
SD=50%	30%	21%	17%	15%	13%

1056Note: The shaded column corresponds to the sample size deemed feasible based on preliminary patient counts1057and financial constraints. Forty (40) participants from Vision Cohorts 1 and 2 will be followed for1058progression

1058 progression.

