#### Data to consider for evaluating sample size: 1109

- Valproic Acid Protocol (VPA) Data (phase II multiple sites, randomized, placebo-1110 1111 controlled trial of oral valproic acid for ADRP) [Placebo group N=44; dataset can be accessed at https://public.jaeb.org/ffb/stdy] 1112
  - Percent Change from Baseline to 1 year, Mean (SD):
- 1114

1113

1118

1120

- -0.3% (16%) OD -4.9% (17%) OS
- 1115 1116 **Assumptions made:**
- Expect average annual decline due to *OAT* will be 5% per year or 20% by four (4) years. 1117
- True SD of percent change at four (4) years is like VPA 1-year SD of approximately 20%. 1119

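### Does the 50% agreement rule for the two baseline microperimetry tests let through errors that undermine the planned change estimates?

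*Protocol*

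**What the plan says.** Vision Cohorts 1 and 2 have two microperimetry tests at Baseline. Under Protocol 3.3.1, item 12, the pair passes if the difference between the two "tests divided by the average between them is $\leq 50\%$ OR the absolute value of the" difference is no more than 0.5 dB. A pair that fails both limbs leads to a third test. Nothing is excluded or discarded. At follow-up, 4.4.1 simply lists "14. Fundus guided microperimetry", with no repeat test.

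In the analysis (8.3.1, item 1(a)i), tests "performed multiple times per visit will be analyzed using the average" of all available results. The annual rate of progression comes from a mixed effects model fitted to the baseline and all annual visits.

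For planning, 8.2.4 assumes that the average decline "will be 5% per year or 20% by four (4) years" and that the "True SD of percent change at four (4) years is like VPA 1-year SD of approximately 20" percent. Section 8.2.1 says the calculations may be used for "percent change on any outcome measure from baseline to four (4) years", so microperimetry is within their reach.

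**The concern.** A check that tolerates a gap of half the average seems loose beside an expected change of 20%. A poor first test could pass, pull the averaged baseline down by 20%, and cancel the full expected decline in that eye. Follow-up has no repeat test, so the baseline pair is the only stated agreement check on this outcome. The neighbouring static perimetry check uses a fixed 2.4 dB, whereas the microperimetry allowance grows with sensitivity.

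There is also a possible conflict between two of the plan's figures. If 50% describes how far two tests on the same eye normally differ, test noise alone could use up the planning SD of 20%. The 6% half-width at 40 participants would then be optimistic for this outcome. The study is meant to supply variability figures for a future trial and to identify rapid progressors, so both points would matter if they held.

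**Working it through.** **Planning figure.** Inputs: SD 20%, effective n 44 (8.2.4). Half-width = 1.96 × 20/√44 = 5.91%, printed as 6%. With SD 30%: 1.96 × 30/√44 = 8.86%, printed as 9% in Table 6.1.

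**What the rule passes.** Let the tests read T and xT. The relative limb is met when (1 − x)/((1 + x)/2) ≤ 0.5, so x ≥ 0.75/1.25 = 0.60. One test may be 40% low, and the average is (1 + 0.60)/2 = 0.80 of T. This holds for averages above 1 dB (T above 1.25 dB). Below that the 0.5 dB limb is looser: at T = 1 dB one test may be 50% low and the average 25% low.

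The rule works in both directions. A test at T/0.6 = 1.67T also passes against T and gives a baseline of 1.33T, 33% too high.

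**Effect in one eye at the limit.** With a true decline of 5 points a year, the visits read 0.80, 0.95, 0.90, 0.85, 0.80.
- Two-point change: 0.80/0.80 − 1 = 0%.
- Least-squares slope over five visits: [−2(0.80) − 0.95 + 0.85 + 2(0.80)]/10 = −0.01, that is −1 point a year. Without the error it is [−2(1.00) − 0.95 + 0.85 + 2(0.80)]/10 = −0.05.

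The slope is strongly attenuated but not zero, and the rise at 12 months stands out.

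**Effect on the group.** The protocol gives no noise figure for the device, so I assume a per-test coefficient of variation (CV) of 10%, 15% or 20% with symmetric errors, and apply the relative limb (one million simulated eyes each).
- Eyes that pass with an average at least 20% low: 0.2%, 2.7%, 6.3%.
- Mean baseline relative to truth: 1.0001, 1.0005, 1.0019, so at most 0.2% off.
- Contribution to the standard error over 44 effective eyes: 1.1%, 1.6%, 2.1%.

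Dividing by a noisy baseline adds a small bias to a mean percent change, about 0.8 times the variance of the baseline average. At CV 20% the SD of that average is 0.0209 × √44 = 0.139, so the bias is about 0.8 × 0.139² = 0.015, or 1.5 points. At CV 10% it is 0.8 × (0.0107 × √44)² = 0.004, or 0.4 points. Any percent change from a noisy baseline has this property, whatever the limit for a third test.

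**The 50% against the 20% SD.**
- Read as a 95% limit: SD of the pair difference 50/1.96 = 25.5%; per test 25.5/√2 = 18.0%; noise in change from two baseline tests and one follow-up test 18.0 × √1.5 = 22.1%. Simulating the rule gives 18.2% (with a 20% decline) to 22.8% (no decline).
- Read as a 99% limit: per test 13.7%; simulated noise in change 13.7% to 17.2%.

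The first range straddles 20% and the second lies below it. The protocol calls 50% neither of these; it is only the trigger for a third test.

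**An SD near 30% is not derivable.** Adding the two sources, √(22.1² + 20²) = 29.8%, counts noise twice. The 20% is modelled on observed SDs of percent change of 16% and 17% in another trial's placebo group (8.2.4), and an observed SD already contains test noise.

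**The case for a change.** The strongest case for the concern is that the arithmetic is exact, that the protocol prints no basis for 50%, and that the study's purpose depends on individual change. Objective 3 summarises change from baseline to four years, and in that two-point measure the worst-case eye does read 0%. Binary progression outcomes would be blurred in the same way. If 50% were a 95% repeatability limit, the 20% SD would leave little or no room for true variation between eyes.

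The algebra stands, and so does the blurring of individual change. The check also cannot detect two tests that are low together. But the consequence is extra noise. Objective 3 tabulates and regresses change by risk factor, with a stated caution about low power; it does not classify single eyes. An understatement of 0.4 to 2.0 points in the mean decline (20 points × 2% to 10% of eyes) would need every large error to be downward and an assumed share of affected eyes. With a per-test SD of 16.3% or 18%, the chance that at least one of two tests is 40% low is about 1.4% or 2.6%, and upward errors offset these.

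The missing rationale is not a fault in the document. Section 3.3 refers test procedures to the Manual of Procedures, which is not at hand. The contrast with static perimetry proves nothing either: the instruments differ, and 50% equals 2.4 dB at an average of 4.8 dB.

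**Conclusion.** The concern does not hold. The rule does pass a pair at T and 0.6T, but it is a coherent trigger for a third test: a relative limit with an absolute floor, which removes no data. The protocol does not contradict itself here, and nothing in it shows 50% to be wrong. Setting a 20% baseline shortfall against a 20% decline compares the extreme of one eye with a population mean. Under symmetric error with an assumed CV of 10% to 20%, the mean baseline shifts by at most 0.2%, and the ratio effect on mean percent change is roughly 0.4 to 1.5 points, against a half-width of 6%.

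The tension with the planning SD depends on an interpretation the protocol does not give. The SD is openly listed as an assumption, 8.2.4 says that rates of decline on these measures are unknown, and Table 6.1, headed "Sample size versus half width of 95% confidence interval for the mean percent change for varying standard deviation values", covers SDs of 20% to 50%. Microperimetry is not a primary outcome. A reader may fairly ask where the 50% comes from, but no answer would change the testing, the averaging or the conclusions. This rests on test errors being roughly symmetric and on the assumed CV range, since the protocol gives no repeatability figure.
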